2. To evaluate the effect of an avatar-based education application on patients' responses to heart attack symptoms and healthcare service utilisation.
3. To compare the effect of an avatar based education application (aimed at improving patients' knowledge of and response to heart attack symptoms), between patients with low health literacy level and patients with an adequate literacy level.

Southern Adelaide Clinical Human Research Ethics Committee

Proposed Methods

1. Study design

A pragmatic randomised controlled trial design, with two parallel groups, will be used to achieve the study's aim.

2. Study duration 1 January 2016 to 30 December 2017

3. Participants

Potential participants will be identified by the nursing shift coordinator, during their hospital stay in the Cardiac Care Unit (CCU) of Flinders Medical Centre. Once consented, participants will undergo a screening phase to assess their eligibility. The study design will include a six-month follow-up period. It is anticipated that approximately 25 participants per week will be recruited.

4. Inclusion criteria and exclusion criteria

Inclusion Criteria	Exclusion Criteria

○ Admitted with any cardiac diagnosis where chest pain or other heart attack symptoms have been experienced previously○ Clinically stable*○ Normal cognitive function○ Sufficient English language ability to communicate and to follow the study procedure	
○ Clinically unstable○ Cognitive impairment○ Failure to give informed consent

*Clinically stable is defined as the achievement of five normal vital signs (i.e. heart rate, systolic blood pressure, respiratory rate, oxygen saturation, and temperature) plus normal mental status and ability to eat, for at least 24 hours prior to enrolment in the study.

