Details about each study measurement will be provided in a later section of this document. The Trial schema is illustrated in Figure 2.

8. Outcomes

Primary outcome

- Knowledge of heart attack symptoms as assessed by the Knowledge sub-scale of the ACS Response Index [30].

Secondary outcomes

- Attitudes and beliefs sub-scales of the ACS Response Index [30].
- Response to heart attack symptoms as assessed by the investigator-developed questions based on the Heart Foundation Heart Attack Action Plan [31]. (See Attached Heart Attack Action Plan Survey)
- Health Services Utilisation as assessed by the investigator-developed questions.(See attached Health Services Utilisation Survey)
- Participants' satisfaction as assessed by SAVE Satisfaction Questionnaire (adapted from two validated surveys) [32,33].

Southern Adelaide Clinical Human Research Ethics Committee

[figure not shown]

Figure 2: Trial schema

Southern Adelaide Clinical Human Research Ethics Committee

9. Study measurements

The mini mental state examination (MMSE)

The MMSE is the most commonly used instrument for screening cognitive function [34]. This examination is not suitable for making a diagnosis but can be used to indicate the presence of cognitive impairment, such as in a person with suspected dementia or following a head injury. The following cut off levels be used for classification purposes: normal cognitive function =27-30, mild cognitive function impairment = 21-26, moderate cognitive function impairment = 11-20, and severe cognitive function = 0-10 [32]. The MMSE will be used in this study to evaluate potential participants' cognitive function, as a part of assessing their eligibility.

Clinical and Demographic data

Information on the study participants' age, gender, education, domiciliary and employment status, medical history, clinical status, past procedures, other admissions, vital signs, and cardiac biochemistry, including in-hospital risk score (GRACE Risk Score) [28], will be collected at baseline.

The Global Registry of Acute Coronary Events Risk Score (GRACE Risk Score)

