The GRACE Risk Score [28], designed to predict in-hospital mortality, was developed from an earlier cohort of GRACE patients. The components of the GRACE RS are age, history of heart failure, history of acute myocardial infarction, heart rate at admission, systolic blood pressure at admission, ST segment deviation, serum creatinine at admission, and elevated troponin and cardiac arrest at admission. In this proposed study, the GRACE Risk Score will be used to provide information on participants' clinical status at baseline.

Rapid Estimate of Adult Literacy in Medicine – Short Form (REALM-SF)

The REALM-SF [35] provides researchers with a brief, validated instrument for assessing patient literacy in diverse research settings in the healthcare system. It has been widely used in the healthcare settings. In the proposed study, the REALM-SF will be used to assess the health literacy level of study participants at baseline.

Acute Coronary Syndrome Response Index (ACS Response Index).

The ACS Response Index [30] is a validated instrument for assessing patients' knowledge, attitudes and beliefs about heart attack symptoms. It includes 21 knowledge subscales, six attitudes subscales and seven beliefs subscales. In the proposed study, the ACS Response Index will be used to assess the knowledge, attitudes and beliefs regarding heart attack symptoms of the study participants.

Heart Attack Action Plan Survey

The Heart Attack Action Plan Survey is an investigator-developed questionnaire for assessing participants' response to heart attack symptoms. It is adapted from the Heart Foundation's Heart Attack Action Plan, including participants' symptoms experiences and their behavioural

Southern Adelaide Clinical Human Research Ethics Committee

responses (STOP, TALK and CALL) (Figure 3) [31]. This information will be collected at baseline, one-month and six-month follow-ups. The purpose of this questionnaire is to evaluate the effect of the app on participants' response to heart attack symptoms.

Figure 3 Heart Attack Action Plan

Health Services Utilisation

Health Services Utilisation is an investigator-developed questionnaire for assessing participants' health-behaviour (including emergency services or GPs). This information will be collected at baseline, and at one-month and six-month follow-ups. The purpose of this questionnaire is to evaluate the effect of the app on participants' response to heart attack symptoms.

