Simple avatar-based Application for ImproVing Heart Attack Education (SAVE)-Satisfaction Questionnaire

Intervention Satisfaction Questionnaire is a 15-item Likert scale. This survey is adapted from validated education material acceptability surveys [32, 33]. The aim of this survey is to assess the participants' perception of the avatar-based education application in terms of audio-visuals, content, usefulness and user-friendliness.

Southern Adelaide Clinical Human Research Ethics Committee

7. Statistical analysis (including justification of sample size, if relevant):

Sample size

The change in the knowledge sub-scale of the ACS Response Index [30] between the control and the intervention groups in a previously published study was used to calculate the required sample size [36]. A sample size calculation was performed using a standard deviation of 2.9 and an effect size of 0.42 for ACS Response Index, which was determined from a previously published study [36]. The required sample size per group was calculated to be 31 ($\alpha=0.05$, power=0.95) this calculation was performed using the independent sample t-test and test by Power Analysis and Sample Size (PASS) software [37, 38]. When taking into account a 10% attrition rate, 70 participants (35 per group) must be enrolled in the study.

8. Recruitment and randomisation

Recruitment

The research nurse will not approach potential participants directly. Potential participants will be identified during their hospital stay in the CCU at Flinders Medical Centre by the nursing shift coordinator. The inclusion and exclusion criteria will be provided to the nursing shift coordinator. The nursing shift coordinator will identify potential participants and obtain their permission to be contacted by the research nurse, as well as the patient's preferred time to be contacted. With the patient's permission, a research nurse (JT or [name]) will approach the patient with the nursing shift coordinator to provide the Patient Information and Consent Form (PICF) and to further explain the purpose and the protocol of this study.

Once consent is obtained, participants will undergo a screening phase to assess their eligibility. Based on current admission statistics it is anticipated that approximately 25 participants per week will be recruited. A study log will be maintained where all individuals screened and their reasons for not participating will be documented.

Randomisation

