Descriptive statistics will be used to summarise the baseline demographic, clinical status, health literacy and mental status of participants. Continuous data will be summarised using mean, median, standard deviation and standard error of the mean scores, whilst categorical data will be summarised in terms of percentages. The demographics of the participants in the intervention and usual care groups will be compared using the independent sample t-test or Pearson's Chi-square test, to measure differences including age and gender. Continuous data with normal distribution will be analysed using the independent t-test, and the Mann-Whitney U test will be used for non-normally distributed data. Association between categorical data will be analysed using the Chi-square test. When comparing the change in ACS Response Index subscale scores overtime and between groups, ANCOVA will be used. The Mann-Whitney U test will be used for data that does not meet the assumptions of ANCOVA. Statistical significance will be considered at $P < 0.05$ unless otherwise specified. All test result reported will be two-tailed. Data analysis will be supervised by a statistician who is not involved in the screening, recruitment or follow-up of the study participants.

Assessment of Participants

1. Clinical Assessment (Medical record review):

Routine clinical data includes: height and weight, previous medical history, risk factors, past cardiac procedure, smoking status, past admission in previous 12 months, GRACE Risk Score, Charlson index of comorbidity, vital sign and cardiac biochemistry.

2. Pathology: Participants will not undertake additional laboratory tests for this project. Cardiac biochemistry will be recorded. Cardiac biochemistry will not be done specifically for this research.

3. Other (e.g. radiological) Assessment: Participants will not undertake other assessment.

4. Monitoring adverse effects

Serious Adverse Effect (SAE) will be defined as any untoward medical, emotional, psychological occurrence resulting in hospitalisation or prolongation of hospitalisation, SAE will be defined as any untoward occurrences in study participants, potentially related to

Southern Adelaide Clinical Human Research Ethics Committee

implementation of the study protocol. Information regarding SAE will be collected during telephone follow-ups.

5. Significant adverse effects should be reported to the Southern Adelaide Clinical Human Research Ethics Committee (SAC HREC)

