SAEs for clinical research study at Flinders Medical Centre site will be reported to the Southern Adelaide Clinical Human Research Ethics Committee (SAC HREC) via the Executive Officer within 48 hours of the event becoming known to the local investigator.

Research relating specifically to the Aboriginal community:

This study is not specifically related to Aboriginal community.

Important information for researchers intending to undertake research in South Australian schools. N/A

Researcher indemnity

Please see attached documentation from the Insurance Officer, Flinders University

Registration of Clinical Trials N/A

Administrative Aspects

1. Name of a contact person, the company name and the ABN of the commercial sponsor MUST be included on page 1. A commercial sponsor is the organisation or company that will be invoiced for the SAC HREC review of this application

[name] is the contact person for this study.

This study is not commercially sponsored.

2. Provision of source and details of funding (Grant, investigator driven, CTG) including payment per participant.

N/A

3. Clinical data sheets

The following documents are attached with your application:

1. Baseline assessment form (Demographic and Clinical information, GRACE Risk Score, MMSE, REALM-SF, ACS Response Index, Heart Attack Action Plan Survey, and Health Services Utilisation)
2. Post intervention survey for intervention group (ACS Response Index, and SAVE Satisfaction Questionnaire)
3. One-month follow-up form (ACS Response Index, Heart Attack Action Plan Survey, and Health Services Utilisation, SAVE Satisfaction Questionnaire)
4. Six-month follow-up form for intervention group (ACS Response Index, Heart Attack Action Plan Survey, Health Services Utilisation, and SAVE Satisfaction Questionnaire)

Southern Adelaide Clinical Human Research Ethics Committee

5. Six-month follow-up form for usual care group (ACS Response Index, Heart Attack Action Plan Survey, and Health Services Utilisation)

4. Maintenance of records

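### Health Services Utilisation is measured before randomisation, but the general tests that would apply to it make no use of the baseline value: a minor loss of precision on a secondary outcome

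*Protocol*

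**What the plan says.** - **Objective.** Specific objective 2 in section 3 is "To evaluate the effect of an avatar-based education application on patients' responses to heart attack symptoms and healthcare service utilisation".
- **Outcome.** Section 8 (Outcomes) lists among the secondary outcomes "Health Services Utilisation as assessed by the investigator-developed questions".
- **Timing.** Section 9 (Study measurements) says of this questionnaire: "This information will be collected at baseline, and at one-month and six-month follow-ups". It is also on the baseline form listed under Administrative Aspects, item 3: "Baseline assessment form (Demographic and Clinical information, GRACE Risk Score, MMSE, REALM-SF, ACS Response Index, Heart Attack Action Plan Survey, and Health Services Utilisation". The section on randomisation places allocation after the baseline assessment, so the baseline value cannot be affected by group.
- **Analysis.** Section 11 (Statistical methods) says "When comparing the change in ACS Response Index subscale scores overtime and between groups, ANCOVA will be used". Its remaining rules go by type of data: "Continuous data with normal distribution will be analysed using the independent t-test, and the Mann-Whitney U test will be used for non-normally distributed data", and "Association between categorical data will be analysed using the Chi-square test". No sentence names a test for Health Services Utilisation, and none of the general rules mentions a baseline term.

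**The concern.** Two sets of outcomes share the same baseline, one-month and six-month schedule, yet section 11 plans baseline adjustment for only one of them, and no reason is given. Utilisation falls to a t-test, a Mann-Whitney U test or a Chi-square test, none of which takes a covariate. A statistical analysis plan that followed section 11 literally would set aside a pre-randomisation measurement that the trial already holds.

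What is at stake is precision. The planned groups are small, about 31 per group after attrition. If earlier use predicts later use, part of the scatter in follow-up utilisation could be removed at almost no cost. The choice is also better fixed in advance: in an open-label trial it should not be possible to pick between adjusted and unadjusted results after seeing them.

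**Working it through.** **Inputs**
- Analysed number: 31 per group (protocol, sample size paragraph). The attrition step reproduces: 31 / 0.9 = 34.4, rounded up to 35 per group, 70 in total.
- The protocol states no effect size, SD or power for utilisation. Its planning figures are for another outcome: "A sample size calculation was performed using a standard deviation of 2.9 and an effect size of 0.42 for ACS Response Index". They are not used below except as a labelled benchmark. Whether 31 follows from them is a separate matter; here 31 serves only as the number analysed.
- Correlation rho between baseline and follow-up utilisation: not in the protocol. Assumed range 0.1 to 0.7.

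**Continuous score.** In units of the outcome SD, the unadjusted difference in means has standard error sqrt(2/31) = 0.254. Linear adjustment for baseline multiplies the residual variance by 1 − rho², so the standard error becomes 0.254 × sqrt(1 − rho²). The equivalent unadjusted sample is 31 / (1 − rho²).

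| rho (assumed) | variance factor | standard error (SD units) | equivalent n per group |
|---|---|---|---|
| 0 | 1.00 | 0.254 | 31.0 |
| 0.1 | 0.99 | 0.253 | 31.3 |
| 0.3 | 0.91 | 0.242 | 34.1 |
| 0.5 | 0.75 | 0.220 | 41.3 |
| 0.7 | 0.51 | 0.181 | 60.8 |

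**Cost of estimating the slope.** With N = 62 and a roughly normal covariate, the expected variance is also multiplied by 1 + 1/(N − 4) = 59/58 = 1.017. At rho = 0.1 the net factor is 0.99 × 1.017 = 1.007, which is no gain. Break-even is where 1 − rho² = 58/59, that is rho = sqrt(1/59) = 0.13. At rho = 0.3 the net factor is 0.91 × 1.017 = 0.93, and at 0.5 it is 0.75 × 1.017 = 0.76.

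**If the t-test were applied to change scores.** Section 11 does not say this for utilisation, but it does not exclude it. With equal SDs at the two times, the variance factor is 2(1 − rho): 1.8 at rho = 0.1, 1.4 at 0.3, 1.0 at 0.5 and 0.6 at 0.7. Below rho = 0.5 this is worse than ignoring baseline. Because 1 − rho² = (1 − rho)(1 + rho), it never beats covariate adjustment, apart from the small slope cost above.

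**Benchmark power.** If 0.42 is borrowed as a standardised difference, power at 31 per group, two-sided 0.05 (normal approximation, slope cost ignored), is 38% unadjusted. Adjusted, it is 38%, 41% and 48% at rho = 0.1, 0.3 and 0.5.

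**Yes/no item.** The table does not carry over to logistic regression. A simulation with 31 per group, assumed rates of 30% and 48%, likelihood-ratio tests and 1,500 runs per setting gave a power gain from baseline adjustment of about 0 to 3 points at baseline to follow-up correlations of 0.1 to 0.3, and about 10 points at 0.5. All these inputs are assumptions.

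**The case against.** **The rules are generic.** Section 11 never names Health Services Utilisation, so the unadjusted analysis is an inference from rules by data type. That is right, and the point is worded accordingly. Yet each test it could fall under lacks a baseline term, and change over time is mentioned only for the ACS Response Index.

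**Covariates for a secondary outcome belong in the analysis plan.** Often so, and that plan is not shown. But section 11 does not leave the tests open: it states them, and it says where ANCOVA applies. The point is that a better method is available for an analysis the protocol does state. It is not that detail is missing.

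**There is no bias.** This stands in full. A reader might infer that, without stratification on earlier use, a chance imbalance would distort the estimated effect of the app, as a second harm beside lost power. The documents do not support that. Randomisation follows baseline, so the unadjusted comparison is valid, and its standard error already allows for chance imbalance. It is the same loss of precision described twice.

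**The size is unknown.** This also stands. A reader might take the benchmark power as the trial's loss on utilisation. It is not: 0.42 belongs to the ACS Response Index, rho is assumed, and the formula is for a continuous score. The items, scale and recall period are not in the text at hand. Baseline is taken during a Cardiac Care Unit stay, so reported use may centre on the index admission and predict later use weakly.

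**The scope is too narrow.** The Heart Attack Action Plan Survey, the other half of Objective 2, has the same schedule and falls under the same general rules. That argues for covering both, not for leaving either out.

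**Conclusion.** The point holds as a minor matter of efficiency on a secondary outcome. Read as written, section 11 would compare utilisation between groups without a baseline value the trial has collected. The result would be valid but possibly less precise than necessary. For a continuous score the reduction in residual variance is 1% at rho = 0.1, 9% at 0.3 and 25% at 0.5. Below about rho = 0.13 there is no net gain at this sample size. The size rests wholly on an assumed correlation and on the scale of the items, neither of which the text at hand gives. It does not show that any conclusion of the trial would change, and it has no bearing on the primary outcome.

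**What to change.** In section 11, state that the between-group comparison of Health Services Utilisation at each follow-up will adjust for the participant's baseline utilisation, with a model suited to the item: ANCOVA for a score, a count model (negative binomial or quasi-Poisson) for numbers of contacts, and logistic regression for yes/no items. Keep the unadjusted test as a supporting analysis, and name it in advance as the fallback if events are too few for the model to be stable. The same sentence can cover the Heart Attack Action Plan Survey.

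Cost: a sentence or two of text and a little more analysis work. No new data, visits or participants are needed. The downsides are small: one degree of freedom, possible instability for sparse items at about 31 per group, and the need to fix the scale of the covariate if the baseline and follow-up forms cover different recall periods.
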